**Elimination of Premature Ventricular Contractions in
Heart Failure (EVAC-HF)**

NCT 01757067

9-17-2011

Elimination of Premature Ventricular Contractions in Heart Failure (EVAC-HF)

Data Analysis

Primary Endpoint

Left ventricular ejection fraction

Based on previous observational data, a minimum 10 percent improvement of EF is expected with successful reduction of PVC burden. We expect a successful suppression of $\geq 80\%$ of PVC's in 60% of patients. We assume an attrition rate of 10% without 6 months follow-up data (in those cases of missing data the enrollment EF will be used as 6 month EF as well). As a result we expect a $10\% \times 0.6 = 6\%$ change of EF, which after accounting for a 10% attrition rate results in a $6\% - 0.6\% = 5.4\%$ improvement of EF in the intervention group. The standard deviation for echocardiographic LV assessment is assumed to be 7 percent. As primary intention-to-treat analysis, we propose a pilot study with 80 percent power to detect a 5.4 percent improvement in LV systolic function (LVEF at 6 months – LVEF at baseline) between the two groups, at an alpha level of 0.05. Using a 1:1 randomization, we will need to randomize 56 patients (28 in each arm) to complete our assessment. Each study site will be allowed up to 10 participants. Randomization will be assigned via email contact with the coordinating site, University of Maryland Medical Center. The Permuted Block design will be utilized in assuring even distribution to the 2 arms of the study.

Fixed Scenario Elements	
Distribution	Normal
Method	Exact
Group 1 Weight	1
Group 2 Weight	1
Number of Sides	2
Null Difference	0
Alpha	0.05

Computed N Total					
Index	Mean Diff	Std Dev	Nominal Power	Actual Power	N Total

9	5.4	7	0.8	0.809	56
---	-----	---	-----	-------	----

A prespecified “on successful treatment” analysis will be performed comparing patients with successful $\geq 80\%$ PVC suppression with patients with unsuccessful PVC suppression.

In case of missing data due to loss of follow-up the enrollment EF will be used as the EF at 6 months assuming no improvement.

Patients in the OMT group that had to cross-over to the ablation group will be analyzed in the OMT group for the intention-to-treat analysis.

Start of anti-arrhythmic drug therapy in the OMT group during the 6 months randomized period is expected to occur only in very rare cases (as patients were stable in 3 months optimization phase). As AAD are often not able to achieve significant PVC suppression, these patients will be analyzed in the OMT group. Uptitration of the HF medications such as beta-blocker is expected to occur only occasionally as they were optimized in the 3 months run-in period. This would be counted as protocol deviation as they could result in improvement of EF independently of studied PVC reduction strategies.

Each value will be measured as the absolute change between baseline and end follow-up and compared between the 2 study groups. All echocardiographic measurements will be made by single echocardiography core center and will include calculation of left ventricular volumes and function using Simpson’s biplane method. Before and after echocardiograms will be reviewed by a single, experienced reader in a blinded fashion.

Secondary Endpoints:

A secondary primary endpoint will include

- a) Echocardiography:
 - Left Ventricular end-systolic volume index (LVESVI)
 - Left Ventricular end-systolic dimension
 - Left Ventricular end-diastolic volume
 - Left Ventricular end-diastolic dimension

All the above echocardiographic parameters assess different aspects of the cardiac function and have been used in clinical studies before.
- b) Biomarker: BNP, hs-Troponin, galectin-3, soluble ST2

All the above biomarkers assess a different pathological pathways/processes which could lead to worsening heart failure. BNP has been associated with heart failure exacerbations and morbidity. Troponin has been related to myocardial necrosis and mortality. Galectin-3 and ST2 have been associated with cardiac fibrosis and remodeling.
- c) Heart Failure: 6-MWT, Kansas City Cardiomyopathy Questionnaire, Minnesota Living with Heart Failure Questionnaire, (possibly SF 12/36)

Very few data is known about the quality of life of this patient population. Therefore the objective is to assess if the intervention (ablation \pm

antiarrhythmic drug for suppression of PVCs) resulted in a change of the quality of life assessed by validated questionnaires compared to the control group.

The objective is to assess if the intervention (ablation ± antiarrhythmic drug for suppression of PVCs) resulted in a change of these parameters compared to the control group.

For each of the patients the difference of the test will be calculated to determine the delta between pre and post. We will then compare the mean between the deltas in the control and intervention group using a t-test. We assume that suppression of PVCs by >80% will result in a significant difference between pre/post measurements compared with the control group.

Specific data to be collected:

- 1- Patient demographics (not identified)
- 2- Peripheral blood samples will be collected and stored from the time of randomization and at 6 months. These samples will be sent to core laboratory and assayed for relevant biomarkers including BNP, galectin-3, soluble ST2.
- 3- Blood samples will be collected at initial visit for genome analysis
- 4- Echocardiographic and electrocardiographic data
- 5- 24 hour Holter recordings with available HRV data
- 6- Procedural data such as 3-dimensional left ventricular mapping data including number and origin of PVCs and the successful ablation sites
- 7- Peri-procedural data collection including mode of sedation, inducibility, dose of sympathomimetic drugs, procedure duration and fluoroscopy time
- 8- The complications, if any, of the procedure
- 9- The acute and intermediate-term success rate of the procedure.
- 10- Procedure, medication and outpatient visit costs
- 11-6 MWT at baseline and 6 months
- 12-Heart Failure Questionnaire at baseline and 6 months
- 13-Clinically performed high-resolution CMRI studies performed prior to the enrollment, during randomization duration and after 6 months will be collected to assess anatomic, perfusion and delayed enhancement myocardial fibrosis.
- 14-Tissue samples that may become available during the study duration from clinically indicated procedures such as biopsy, LVAD placement or heart transplantation will be stored for further tissue analysis
- 15-Clinical data such as past medical history, medications, NYHA class, physical exam findings, hospitalizations will be assessed during the 2-years follow-up

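### Does the undefined standard deviation of 7 undermine the 56-patient sample size?

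*SAP*

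**What the plan says.** All of this is in the SAP under Data Analysis, Primary Endpoint, except where noted. The protocol has no sample-size text.

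- **Mean difference.** The SAP states that "a minimum 10 percent improvement of EF is expected with successful reduction of PVC burden", expects successful suppression in 60% of patients and assumes 10% attrition. Dropouts are handled by carrying the baseline value forward: "in those cases of missing data the enrollment EF will be used as 6 month EF as well". This gives 10 × 0.6 = 6, less 0.6, or 5.4 EF points.
- **Standard deviation.** "The standard deviation for echocardiographic LV assessment is assumed to be 7 percent". No source is attached. The reference to earlier observational data belongs to the 10-point gain only.
- **Target.** "we propose a pilot study with 80 percent power to detect a 5.4 percent improvement in LV systolic function", two-sided, "at an alpha level of 0.05", with 28 patients per arm. The table prints a mean difference of 5.4, an SD of 7, a total of 56 and an actual power of 0.809.
- **Analysed variable.** "Each value will be measured as the absolute change between baseline and end follow-up and compared between the 2 study groups". At the end of the Secondary Endpoints section the test is named: "We will then compare the mean between the deltas in the control and intervention group using a t-test".

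**The concern.** Two features of the SD invite the question. First, its description fits several quantities: the spread of a single EF reading, measurement error, the SD of the six-month change among patients with the same suppression outcome, or the overall SD of that change. Only the last belongs directly in a t-test on changes.

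Second, the SAP carries its 60% success rate and 10% attrition into the mean but does not mention the variance they create. On its own assumptions 54% of the ablation arm gain 10 points and 46% gain none. That mixture has a spread of its own, and if 7 leaves it out, the true SD of the analysed change is larger than the one entered.

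At stake is whether 56 patients meet the plan's 80% power target. At 28 per arm and a difference of 5.4, 80% power requires an overall SD of no more than 7.08, so the entered value leaves little slack.

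**Working it through.** **Method.** Two-sample t-test power from the noncentral t distribution, two-sided alpha 0.05, n per arm, 2n − 2 degrees of freedom and noncentrality d / (s × √(2/n)). Where the arms differ in variance, s is the root mean square of the two arm SDs.

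**1. The plan's own figure.** Inputs from the SAP: d = 5.4, s = 7, n = 28.

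- Noncentrality = 5.4 / (7 × √(2/28)) = 2.886; critical t on 54 df = 2.005; power = 0.809.
- With 27 per arm, power = 0.794, so 28 per arm is the smallest balanced size that reaches 80%.

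The table is reproduced exactly.

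**2. If 7 excludes the success/non-success spread.** Inputs from the SAP: gain 10 in successes and 0 in the rest; success 0.6; follow-up 0.9; dropouts have a change of exactly 0 under the carry-forward rule.

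- Share gaining 10 points: 0.6 × 0.9 = 0.54. Mean: 5.4.
- Mixture variance in the ablation arm: 0.54 × 10² − 5.4² = 24.84.
- Ablation-arm variance: 0.9 × 49 + 24.84 = 68.94. OMT-arm variance: 0.9 × 49 = 44.10.
- s = √((68.94 + 44.10)/2) = 7.52. Noncentrality = 2.688. Power = 0.752. Reaching 80% would take 64 patients.

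A simulation of 100,000 trials gave 0.753. A lower figure of 0.716 results if dropouts are also given a change SD of 7, but that contradicts the rule that they keep their enrollment EF, so it is set aside.

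**3. Sensitivity of that shortfall.** Same reading (within-group SD 7, mixture spread included, dropouts at 0), with the gain in successes varied and success held at 60%:

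| Gain in successes | Mean difference | s | Power, 28 per arm |
|---|---|---|---|
| 10 (SAP minimum) | 5.40 | 7.52 | 0.752 |
| 11 (assumed) | 5.94 | 7.69 | 0.810 |
| 13 (low end of the range in the protocol's introduction) | 7.02 | 8.07 | 0.892 |
| 15 (protocol, Justification) | 8.10 | 8.49 | 0.939 |

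The protocol figures are read here as EF points. Holding the gain at 10 and raising success to 65% (assumed) gives 0.818.

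**4. Other readings.**

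- If 7 is the overall SD of change among followed patients and dropouts are set to 0, the arm variances are 0.9 × (49 + 6²) − 5.4² = 47.34 and 44.10, s = 6.76, and power is 0.835.
- If 7 is the SD of a single EF, the SD of change is 7 × √(2(1 − r)), where r is the baseline-to-six-month correlation. The documents give no r. Assumed values of 0.3, 0.5 and 0.7 give power of 0.67, 0.81 and 0.96 without the mixture spread, and 0.63, 0.75 and 0.89 with it.

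The readings fall on both sides of 0.809, so they establish no direction of error.

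**The case for a change.** The strongest case for acting is that the SAP adjusted the mean for success and attrition and was silent on the variance that the same assumptions produce. The mixture contributes 24.84/2 = 12.42, averaged over the arms, out of the 7.083² = 50.17 variance units that 80% power allows, or about a quarter. If 7 is the overall SD in the ablation arm, the SD within each outcome group is only √(49 − 24.84) = 4.9, a value the SAP neither states nor supports. One sentence would settle the matter, and the word pilot does not cancel a claim of 80% power made in the same sentence.

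Part of this stands. The SD has no source, its description is loose, and a sentence defining it would have been good practice.

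The rest does not make a defect. The SAP defines the tested quantity as the six-month EF minus the baseline EF, and the table sets 7 beside a difference in that quantity; used that way, it is the common SD of the change. No text describes an SD within suppression outcomes. The narrow margin is also expected, because 28 per arm was chosen as the smallest size reaching 80%, so any such design sits just inside its SD limit.

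Early crossover adds nothing to the case. The SAP already settles its handling ("Patients in the OMT group that had to cross-over to the ablation group will be analyzed in the OMT group"), and the documents give no rate from which an effect on power could be worked out.

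**Conclusion.** The concern does not call for a change. On the reading that the power table implements, 0.809 and 56 patients are correct. On the least favourable reading that respects the SAP's stated gain, success rate, attrition and carry-forward rule, and takes 7 as an SD of change, power is about 0.75, some 6 percentage points lower. That depends on 7 excluding the success/non-success spread, which the documents do not say, and on a gain fixed at what the SAP calls a minimum; a gain of 11 restores 0.81. The larger gains cited in the protocol give 0.89 and 0.94, although they come from observational reports and may be optimistic.

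What remains is an assumption without a definition or source. Supplying them would alter neither the number randomized nor the analysis, because the t-test estimates its variance from the trial data and not from the planning value. It is a gap in the written justification that a statistician reading the table fills in the ordinary way.

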### **Risks:**

Ventricular tachycardia ablation procedures have a definite morbidity and mortality, with a major complication rate ranging from 2.5 to 6 %. This is due to both patient-related and procedure-related factors. Patients typically suffer from congestive heart failure and other comorbidities and the procedures are long, requiring the patient to lie flat for up to eight hours at times.

In addition to the risks of sedation, standard risks of an endocardial procedure include bleeding and other vascular access complications, stroke, myocardial infarction and rarely myocardial rupture and pericardial tamponade, aortic valve avulsion, and entanglement of the catheter in the mitral valve apparatus requiring surgical intervention, and death. The safety data of PVC ablations is not as well established as for VT ablations. In general, significantly less ablation lesions have to be applied frequently reducing the procedure time and volume administered. Additionally, many PVC ablations can be performed from the RV resulting in less risk of thromboembolic events or groin complications than for left-sided ventricular tachycardia ablations.

Epicardial ablations will have to be performed in a subgroup of patients. This approach has been associated with complications such as RV perforation, coronary artery or phrenic nerve injury or abdominal bleeding.

There are no known significant risks associated with echocardiograms or Holter monitors. There is a slight possibility of skin redness or irritation due to the

placement of the ECG electrodes, which should disappear within several hours of removing the electrodes.

Blood drawing can cause pain, bruising, lightheadedness and, on rare occasion, infection.

There are risks of loss of confidentiality to patients that participate in this trial; however all necessary precautions will be taken to assure the patient's confidentiality is maintained. The information will be kept in secure locations. In any publication or presentation of research results, patient's identity will not be disclosed.

Pregnant females are excluded from participation in this trial because they are not eligible for catheter ablation due to radiation risks to the developing fetus. All females with child bearing potential that want to participate will need to do a pregnancy test the morning of the ablation procedure, and the test must be negative to have an ablation.

Specific data to be collected:

- 1- Patient demographics (not identified)

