- 2- Peripheral blood samples will be collected and stored from the time of randomization and at 6 months. These samples will be sent to core laboratory and assayed for relevant biomarkers including BNP, galectin-3, soluble ST2.
- 3- Blood samples will be collected at initial visit for genome analysis
- 4- Echocardiographic and electrocardiographic data
- 5- 24 hour Holter recordings with available HRV data
- 6- Procedural data such as 3-dimensional left ventricular mapping data including number and origin of PVCs and the successful ablation sites
- 7- Peri-procedural data collection including mode of sedation, inducibility, dose of sympathomimetic drugs, procedure duration and fluoroscopy time
- 8- The complications, if any, of the procedure
- 9- The acute and intermediate-term success rate of the procedure.
- 10- Procedure, medication and outpatient visit costs
- 11- 6 MWT at baseline and 6 months
- 12- Heart Failure Questionnaire at baseline and 6 months
- 13- Clinically performed high-resolution CMRI studies performed prior to the enrollment, during randomization duration and after 6 months will be collected to assess anatomic, perfusion and delayed enhancement myocardial fibrosis.
- 14- Tissue samples that may become available during the study duration from clinically indicated procedures such as biopsy, LVAD placement or heart transplantation will be stored for further tissue analysis

15-Clinical data such as past medical history, medications, NYHA class, physical exam findings, hospitalizations will be assessed during the 2-years follow-up

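### A missing 6-month EF is scored as zero change in the primary analysis, and no planned analysis tests that assumption

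*SAP*

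**What the plan says.** The rule appears twice in the SAP, under Data Analysis, Primary Endpoint. In the sample-size paragraph it applies to the 10% of patients "without 6 months follow-up data (in those cases of missing data the enrollment EF will be used as 6 month EF as well". Later in the same section it is repeated for one reason: "In case of missing data due to loss of follow-up the enrollment EF will be used as the EF at 6 months". Both sentences give the same imputation, a change of zero.

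The primary comparison is by intention to treat: "As primary intention-to-treat analysis, we propose a pilot study with 80 percent power" to detect 5.4 EF points. On the test, the SAP says after the secondary endpoints: "We will then compare the mean between the deltas in the control and intervention group using a t-test".

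The only other prespecified EF analysis ("analysis will be performed comparing patients with successful" PVC suppression with those without it) regroups the patients and leaves the missing-data assumption as it is. The rules for cross-over, antiarrhythmic drugs and uptitration in the OMT arm do not deal with missing EF. Neither document contains a complete-case analysis, multiple imputation, a tipping-point analysis or a specific rule for death, LVAD or transplant.

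**The concern.** Zero change is one fixed value assigned to about 5.6 of 56 patients (10%). It is safe when loss is equal in the two arms and the missing patients changed alike. It is not safe when loss is unequal and those patients got better or worse. The direction then depends on which arm lost more and which way its patients moved, and nothing in the plan would show this. The imputed value also cannot separate a death from a missed echocardiogram.

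The Protocol gives some reason to test the assumption. Under Risks it lists "entanglement of the catheter in the mitral valve apparatus requiring surgical intervention, and death" among the hazards of an endocardial procedure, to which OMT patients are exposed only if they cross over. The 6-month TTE is a clinical study timed from enrollment or from the last ablation, so its timing can differ by arm. None of this shows that loss will be unequal.

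At stake is whether a borderline positive result can be defended when a reader asks what happened to the missing patients.

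**Working it through.** **Inputs from the SAP.** Gain of 10 points with successful suppression, 60% success, 10% attrition, SD 7, 28 per arm, two-sided alpha 0.05.

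**1. The plan's own figure.**
- Effect: 10 × 0.6 = 6; 6 × 0.9 = 5.4.
- SE = 7 × √(2/28) = 1.871.
- Power from the noncentral t with 54 df at 5.4: 0.809 (27 per arm gives 0.794). N = 56 reproduces.
- Smallest significant difference: about 3.75.

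**2. Bias when missing patients fell** (loss by arm and size of fall are assumptions). If patients lost in either arm truly fell by w, zero-fill shifts the difference towards ablation by w × (loss in ablation − loss in OMT).
- 10% vs 10%: 0.
- 15% vs 5%, w = 5: 5 × 0.10 = 0.5 point (0.5/1.871 = 0.27 SE); type I error 0.058.
- 15% vs 5%, w = 10: 10 × 0.10 = 1.0 point (0.53 SE); type I error 0.082.
- 5% vs 15%: −0.5 and −1.0.

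The shift favours the arm that lost more.

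**3. Bias when both arms improve** (also assumed). With no true difference and a 4-point gain in both arms, loss of 5% in ablation and 15% in OMT gives 4 × 0.95 − 4 × 0.85 = 0.4 point; simulated type I error is about 0.055. This shift favours the arm that lost less.

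**4. Tipping points.** There are 28 patients per arm. Observed changes are normal scores with SD 7 and OMT mean 0; the gain is the difference in means among patients with a 6-month echo. Missing ablation patients are set to −δ; missing OMT patients are set to 0 or also to −δ. Values can move by about 0.1 with the scaling of the scores.

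| Observed gain | Missing (ablation vs OMT) | Zero-fill difference | p | δ at p = 0.05, ablation only | δ at p = 0.05, both arms |
|---|---|---|---|---|---|
| 6.0 | 3 vs 3 | 6.0 × 25/28 = 5.36 | 0.004 | 11.7 | 20.7 |
| 6.0 | 4 vs 1 | 6.0 × 24/28 = 5.14 | 0.007 | 7.8 | 9.2 |
| 5.0 | 3 vs 3 | 5.0 × 25/28 = 4.46 | 0.016 | 6.3 | 13.5 |
| 5.0 | 4 vs 1 | 5.0 × 24/28 = 4.29 | 0.022 | 3.7 | 4.5 |
| 4.5 | 3 vs 3 | 4.5 × 25/28 = 4.02 | 0.028 | 3.4 | 8.9 |
| 4.5 | 4 vs 1 | 4.5 × 24/28 = 3.86 | 0.037 | 1.4 | 1.8 |

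**5. Events** (illustration only). In 20,000 simulated trials with gain 6, SD 7 and 3 missing per arm, let 0, 1 or 2 of the three missing ablation patients be a death, LVAD or transplant. The planned t-test has power of about 0.84 in all three cases. A Wilcoxon test that ranks those events lowest gives 0.81, 0.73 and 0.65. For scale, the Protocol's only rate, "with a major complication rate ranging from 2.5 to 6" percent, is for all major complications of VT ablation: 28 × 0.025 = 0.7 to 28 × 0.06 = 1.7 patients.

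**6. ANCOVA.** With equal variance at both times and baseline-to-6-month correlation r, the variance of change is 2σ²(1 − r) and the baseline-adjusted variance is σ²(1 − r²). The SE ratio is √((1 + r)/2): √0.65 = 0.81 at r = 0.3 and √0.85 = 0.92 at r = 0.7. If SD 7 is the SD of change, power at 5.4 would be 0.94 and 0.87.

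**The case against.** The strongest reply is that the rule is open and conservative. Under the plan's assumptions it shrinks a true 6-point effect to 5.4, and the sample size was set at 5.4. About 90% of EFs should be observed, and the planned gain survives all but extreme assumptions. The fragile cases have p between 0.016 and 0.037 before any adjustment, and any perturbation matters there. This is also a pilot study. All of that stands, and it limits the weight of the point. It does not replace a check, because the rule is conservative only if the assumptions about loss and change hold.

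Three stronger readings are tempting, and the documents do not support them.

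- A reader might infer from the later sentence, limited to loss of follow-up, that a patient who dies or receives an LVAD or transplant has no rule. Both sentences are in force, they give the same imputation, and the one in the sample-size paragraph covers everyone without 6-month data. The difference is a matter of wording.
- A reader might infer that such events will occur before 6 months and fall on the ablation arm. The Protocol gives no rate for death. It names LVAD and transplant only as sources of tissue ("LVAD placement or heart transplantation will be stored for further tissue analysis"), without dating them. An OMT patient who deteriorates and crosses over does so on a documented EF decrease, so that route involves a measured EF.
- A reader might infer that the rule favours ablation or undermines N. Steps 1 to 3 show neither.

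The Protocol also collects complications and hospitalizations and may contact patients at 1 and 2 years, so the trial record could identify events that the imputed EF hides. Collecting data is not a planned analysis, however.

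**Conclusion.** The point holds as a gap in the analysis plan: a single-value imputation for an expected 10% of a 56-patient primary analysis, with no planned test of it. The sample size and the primary rule can stay as they are.

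In the scenarios worked, the possible bias is 0 with equal loss and equal change, 0.4 point in one direction when both arms improve, and 0.5 to 1.0 point in the other when missing patients fell, against a 5.4-point target. These figures rest on assumed loss by arm and assumed changes in the missing patients, since the SAP does not split the 10% by arm or reason. The practical risk lies in a result somewhat below plan with unbalanced loss. There the conclusion can depend on four missing patients having fallen by 1.4 to 3.7 points, which is well inside the plan's SD of 7.

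This should be changed, with medium confidence. The ANCOVA suggestion is a separate gain in precision, and the point does not depend on it.

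**What to change.** 1. **Wording.** Merge the two SAP sentences: every randomized patient without a 6-month EF, whatever the reason, stays in the primary analysis with the enrollment EF. Patients with death, LVAD or transplant should not be dropped from the mean. With 3 missing per arm and a gain of 6, dropping one or two ablation events would raise the difference from 5.4 to 6 × 25/27 = 5.6 or 6 × 25/26 = 5.8.

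2. **One prespecified sensitivity analysis, with no success condition attached.** Run a delta-adjusted tipping-point analysis in which missing patients change by, for example, −15 to +10 points, varied separately by arm, and report where p crosses 0.05. The grid needs improvements as well as declines, because a decline-only grid would miss the bias in step 3. Report counts of missing EF by arm and reason, including death, LVAD and transplant.

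3. **Optional.** If a worst-rank test is added, count events over the same fixed window from randomization in both arms. A window ending at the 6-month TTE could be longer in the ablation arm, because that TTE may be timed from the last ablation and a repeat procedure is allowed within 6 weeks.

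4. **Separately, for precision.** Analyse the primary comparison by ANCOVA adjusted for baseline EF, which is already collected, in place of the change-score t-test.

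The cost is SAP text and a little programming and reporting, with no added patients, visits or data. The downside is that a sensitivity result may look less favourable than the primary one.
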